1.2 AF SCREENING IN DENTAL CLINICS

Dental clinics provide an ideal location, and an appropriate health professional/community interface, to screen people for AF. Approximately 90% of the UK population visits a dentist every two years making it one of the most accessible healthcare services in the community. Approximately 50% of the adult population have PD, with 30% of the population having treatment for active tooth decay.⁷ Those requiring specialist treatment of periodontal disease attend dental hospitals, thus those at highest risk of cardiovascular disease due to periodontal disease are likely to be found in these clinics. The NHS Newcastle Dental Hospital and School is the preeminent centre for specialist oral health care, education and research in North England. The Dental Hospital is one of the largest integrated teaching and hospital complexes in the UK, which includes 3 community outreach clinics. The Dental Hospital and School provides a range of dental services and a recent audit showed that in one month over 2500 patients over the age of 65 years attended for treatment. We aim to test if dental clinics are a suitable place to identify previously undetected AF during and beyond the COVID-19 pandemic. The study will aim to 1) determine if there is any correlation between severity of dental disease and AF incidence; 2) test a pathway to ensure that patients are appropriately managed following detection of AF; and 3) to determine cost-effectiveness of identification of AF in dental settings.

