2.2 Primary Endpoint/Outcome Measure

The primary outcome measure will be the proportion of screened subjects with newly identified AF attending a dental clinic aged 65 years and older.

STUDY DESIGN

(Phase 1) A cross-sectional study of screening in dental clinics to identify undiagnosed AF in adults aged 65 years and over. (Phase 2) A qualitative study of healthcare professionals involved in the care of phase 1 study participants to explore factors that might influence sustainability of screening processes beyond the study setting.

STUDY POPULATION

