5.1.2 Data analysis

Phase 1: patient screening:

Primary analyses will be conducted using SPSS (V26). New episodes of AF will be expressed as true positives divided by total number screened with accompanying 95% CIs. A sample size of 1000 will provide a CI of 60.8% assuming an incidence of 1.6%. χ^2 tests will be used to compare new cases by sex and to identify associations between AF incidence and age group or AF risk factors. A Pearson's or Spearman's correlation test, depending on normality of data, will be used to assess the strength and the direction of relationships between parameters. A two-sided p value of < 0.05 will be considered significant.

Cost-effectiveness

A previously tested decision-analytic Markov model⁸ will be used to simulate the risk of stroke and bleeding events with standard case finding of newly identified AF (i.e. no screening/usual care) and to then assess the impact that screening with single lead ECG would have on the downstream costs and health outcomes over a 30 year time

Edinburgh Napier

horizon. Costs incorporated in the model will include those associated with screening, drugs to offset the risk of stroke (i.e., warfarin or NOACs), adverse events (e.g., systemic embolism, stroke) and the potential complications of warfarin and NOAC treatment (e.g., intracranial haemorrhage, clinically relevant bleed). Health-state utilities associated with pre and post treatment will be incorporated in the model to calculate QALYs. A ceiling ratio of £30,000 per QALY to delineate the cost-effectiveness of opportunistic screening will be applied. Costs and benefits (QALYs) will be discounted at the NICE recommended rate of 3.5% per annum in line with the NICE reference case. Model inputs will be based on several available evidence sources including previous work in AF screening in Scotland. Extensive deterministic sensitivity analysis along with probabilistic sensitivity analysis will be undertaken to investigate model assumption and parameter uncertainty on robustness of the results.

Phase 2: healthcare professionals' interview:

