12.11 Appendix 11: Patient Screening Document Phase 1 (Version 3:16/8/2022)

	Participant ID:			
	Name			
	Address			
	Postcode (IMD):			
	Date of Birth:			
	Telephone Number:			
	Registered GP:			
	GP surgery address:			
		l		
٧	Vhat sex where you a	ssigned at bir	th?	
	Male			
	Female			
V	What age are you?			
•	viiat age are you:			
٧	Vhat race/ethnic grou	p do you cons	ider yourself	?
	White British			
	White Other			
	Black Caribbean/Black Ca	ıribbean		
	British			
	Black African/Black Africa	an British		
	Indian/Indian British			
	Pakistani/Pakistani Britisl	h		
	Bangladeshi/Bangladeshi	British		
	Chinese/Chines British			
	Filipino/Filipino British			
	Maghreb / Middle Easter	'n		
	Mixed Ethnicity			
	Other (please specify)			
L)o you have / a histor y Heart Failure	y of any of the	following?	
		ا مسمممیسم)		
	Hypertension (high blood	•		
	Stroke/TIA/thromboemb			
	Vascular disease (prior M	• •		
	artery disease or aortic p	iaque)		
	Diabetes			
	Atrial fibrillation			

Are you taking any of the medication b	e low?
Warfarin	
Dabigatran	
Rivaroxaban	
Edoxaban	
Apixaban	
Beta-blocker (ends in IoI)	
Verapamil	
Diltiazem	
Amiodarone	
Flecainide	
Propafenone	
Digoxin	
Other (please specify)	
Do you have any of the following symp	toms?
Heart palpitations	
Chest pain	
Dizziness	
Fatigue	
Light-headedness	
Shortness of breath	
Reduced ability to exercise	
None	
	Screening
KardioMobile ECG Screening	Result
Sinus rhythm	
AF not suspected by abnormal rhythm	
AF suspected	
AF known prior to screening	
Basic Periodontal Examination	Result
Upper right Upper anterior Upper	1
Lower right Lower anterior Lower	
Lower differior Lower	

Appendix 12 : Follow up telephone screening form Phase 1 Study Protocol Date: 25/1/2022 Version: 5

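### The periodontal question is posed as AF incidence, which one cross-sectional ECG cannot measure; it has no stated test and about 16 new cases, and known AF has no place in the analysis

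*Combined protocol and SAP*

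**What the plan says.** The design is "A cross-sectional study of screening in dental clinics to identify undiagnosed AF in adults aged 65 years and over" (Study Design, after section 2.2). Section 4.1 gives each participant a 30-second single-lead recording. A six-lead repeat is offered if the rhythm is abnormal but not AF. The one-month call to those with an abnormal rhythm asks about referral, tests and treatment; it does not look for new onset of AF.

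Section 1.2 nevertheless sets out to "determine if there is any correlation between severity of dental disease and AF incidence". The aim and first secondary objective in section 2.1, and section 2 of the data management plan (Appendix 15), use the same measure.

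Section 5.1.2 holds the whole quantitative plan:

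- Primary proportion: "New episodes of AF will be expressed as true positives divided by total number screened".
- Sizing: "A sample size of 1000 will provide a CI of 60.8% assuming an incidence of 1.6" per cent.
- Associations: chi-square "tests will be used to compare new cases by sex and to identify associations between AF incidence and age group or AF risk factors".
- A Pearson or Spearman coefficient that "will be used to assess the strength and the direction of relationships between parameters".
- "A two-sided p value of < 0.05 will be considered significant".

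Periodontal status is not named in any of these. No effect size or power is given for it.

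Known AF is not an exclusion in section 2.5. It has its own pathway in section 4.1, and Appendix 11 records it as medical history and as a screening result, "AF known prior to screening". No analysis of known or total AF is planned.

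**The concern.** Three things come together. First, incidence needs people free of AF who are followed over time, and nobody here is followed for onset. The evidence cited in section 1.1 is hazard ratios from a cohort without prior AF, so the shared word invites a comparison of unlike measures.

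Second, a stated secondary objective has no named test and no defined outcome. The nearest wording in 5.1.2 concerns new cases, which will be few. With a 0.05 threshold attached, a non-significant result is likely even if the cited association is true, and it could be reported as no correlation.

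Third, the study will record known AF and then not use it. If the base for the comparison is everyone screened, as for the primary proportion, people who have AF would count as people without it.

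**Working it through.** **The plan's own figure.** The 1.96 × √(p(1−p)/n) half-width with p = 0.016 and n = 1000 is 1.96 × √(0.016 × 0.984/1000) = 0.0078, or ±0.8 percentage points. This agrees with the sizing sentence if the printed 60.8 is a garbled ±0.8, which I take it to be. The sizing concerns the primary proportion only.

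**Expected events.**

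- New AF: 1000 × 0.016 = 16. At the 1.44% detection rate in section 1.1 it is 14.4. If 5% already have known AF, 950 × 0.016 = 15.2.
- Total AF: section 1.3 puts AF at about 5% of those aged 65 and over, without saying whether that is diagnosed AF or all AF. If all AF, 1000 × 0.05 = 50 events (50/16 = 3.1 times). If diagnosed AF only, 50 + 16 = 66 (66/16 = 4.1 times). Both assume that people with AF enrol at the population rate, which the documents do not give.

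**Power and precision.** Inputs: 1000 participants; two-sided 0.05; the cited ratios for severe periodontal disease, 1.54 crude and 1.31 adjusted, taken as odds ratios. The exposed share is assumed: 50% (section 1.2 gives this for any periodontal disease in adults) and 30% as a lower value. Total events are held fixed. Power is from a simulated 2×2 chi-square test. SE(log OR) = √(1/a + 1/b + 1/c + 1/d) on the expected cells, and the interval is OR × exp(±1.96 × SE).

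Worked case, 16 events, OR 1.54, 50% exposed: the expected cells are 9.67 and 490.33 exposed, 6.33 and 493.67 unexposed. SE = √(0.1034 + 0.0020 + 0.1580 + 0.0020) = 0.515, so the interval is 0.56 to 4.2.

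| Ratio | Events | Power | SE(log OR) | Typical 95% CI |
|---|---|---|---|---|
| 1.54 | 16 | 13–16% | 0.52 | 0.56 to 4.2 |
| 1.54 | 50 | 31–32% | 0.30 | 0.86 to 2.8 |
| 1.54 | 66 | 39% | 0.26 | 0.92 to 2.6 |
| 1.31 | 16 | 8–10% | 0.51–0.53 | 0.47 to 3.7 |
| 1.31 | 50 | 15–16% | 0.29–0.30 | 0.72 to 2.4 |
| 1.31 | 66 | 18–19% | 0.26–0.27 | 0.78 to 2.2 |

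Taking 1.54 as a risk ratio instead, a normal approximation gives 13–16% with 16 events and 34–44% with 50–66. As a rough guide (Schoenfeld), 80% power at 1.54 needs (1.96 + 0.842)²/[f(1−f)(ln 1.54)²] events: 7.85/(0.25 × 0.1864) ≈ 169 at f = 0.5 and 7.85/(0.21 × 0.1864) ≈ 201 at f = 0.3.

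**Effect of leaving known AF among the non-cases.** Assume 5% known AF with the same odds ratio of 1.54 and 50% exposed. Known AF is then 30.06/500 = 6.0% of the exposed and 19.94/500 = 4.0% of the unexposed. A true new-AF odds ratio of 1.54 among those without known AF becomes about 1.54 × 0.940/0.960 = 1.51 when everyone screened is the base. At 30% exposed it is 1.50. The shift is about 2%.

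**The case against.** The strongest reply is that this is a secondary objective in a study meant to inform larger research. The primary endpoint is correctly worded as a proportion and is unaffected. The rationale in section 1.3 concerns unrecognised AF, so new cases are a legitimate outcome; pooling them with AF diagnosed at any earlier time, against a periodontal score taken now, asks a different question. Nor does pooling rescue the test: even 66 events leave power below 40% at 1.54, with an interval that includes 1. All of that stands. It supports adding total AF beside new AF, not replacing it. It does not remove the mislabelled measure or the missing specification.

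Four stronger readings are tempting but unsupported:

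- *The plan chooses to test periodontal status on new cases.* Section 5.1.2 never says so. It is an inference from the mention of AF risk factors, read with section 2.1; the correlation sentence could equally be meant.
- *Using known AF would quadruple the events.* That is the top of a three- to fourfold range. It needs the 5% to be diagnosed AF only, and the documents do not say that.
- *Known AF among the non-cases seriously biases the result toward the null.* The shift is about 2%. The documents also do not say that these people are counted as non-cases; Appendix 11 gives them their own result category.
- *The mislabel carries into the Markov model as a per-cycle rate.* Section 5.1.2 does not say how the yield enters the model.

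**Conclusion.** The point holds in this form. Incidence is the wrong measure wherever the documents use it for this study's results. The periodontal analysis is unspecified and, on the natural reading, rests on about 16 events. It is then nearly uninformative at the effect sizes the protocol itself cites.

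Known AF is recorded but unused. The main loss is precision, not bias. A total-AF analysis would roughly halve the standard error, but the association would remain exploratory. These sizes assume a 1.6% yield, about 5% known or total AF with enrolment at that rate, 30–50% exposed, and the cited hazard ratios read as odds ratios. The primary objective is not affected.

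**What to change.** - Replace incidence with prevalence of newly detected AF in sections 1.2, 2.1 and 5.1.2 and in section 2 of Appendix 15, wherever it describes this study's outcome.
- In 5.1.2, name the periodontal analysis: how the Basic Periodontal Examination (BPE) codes are summarised per participant, the outcome and the model.
- Analyse newly detected AF, using the case definition of the primary outcome, with known-AF participants removed from the comparison group.
- Add a pre-specified analysis of total AF (known plus new) on BPE, with age and sex in the model.
- Report both as exploratory odds ratios with 95% intervals. State that a non-significant result does not show absence of association.

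The cost is protocol and SAP wording and one further model on data already planned, with no added participants or procedures. There are limits. Known AF is self-reported unless checked. Pooling mixes long-standing with new AF, which is why both outcomes should be shown. BPE comes from routine dental records, so the number with missing results should be reported.

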Periodontal disease (PD) is strongly associated with cardiovascular disease. A recent study highlighted the high prevalence of AF in a population who have PD.⁶ In the dental Atherosclerosis Risk in Communities Study (ARIC) cohort, 5,958 were assessed without prior AF, 754 (13%) were found to have AF.⁶ Severe PD was associated with AF on both univariable (crude HR, 1.54; 95% CI, 1.26-1.87) and multivariable (adjusted HR, 1.31, 95% CI, 1.06-1.62) analyses. Mediation analysis suggested AF mediates the association between PD and stroke. In the main ARIC cohort, 9,666 participants without prior AF were assessed for dental care use, 1558 were found to have AF (16%).⁶

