1.3 RATIONALE FOR STUDY

Date: 30/5/2022 Version: 6

AF is prevalent, affecting approximately 5% of those aged 65 years and older. Unrecognised AF is generally not associated with symptoms and raised resting heart rate. Those with unrecognised AF usually have stroke risk scores (i.e., CHA2DS2 VASc scores) high enough to warrant anticoagulation. Furthermore, registry data suggests that incidence of AF may be much higher in a population who have periodontal disease, which generates the hypothesis that there are appreciable numbers who would benefit from early recognition of AF through simple detection programmes, followed by thromboprophylaxis to prevent future stroke.

This study aims to determine the appropriateness and impact of dentistry-based screening, using innovative technology (a single/six lead ECG device, KardiaMobile) that has been used in numerous AF screening studies, focused on identifying people with undiagnosed AF, with onward referral to their GP for appropriate medical management of AF. The study also aims to explore the role of dentists in ongoing management of AF, as well their role in raising AF awareness in the public.

The findings of this study will have broad implications for the general population aged 65 years and older with undiagnosed AF. We anticipate that the study will demonstrate that it is possible to identify and treat people in the community, not identified due to COVID-19 restrictions, who were not previously known to have AF, thus greatly reducing the risk of stroke. Findings from this study will inform the design and refinement of a future intervention for large-scale research and implementation.

2 STUDY AIM and OBJECTIVES

2.1 **Aim**

The study aims to test if dental clinics are a suitable place to identify previously undetected AF during and beyond the COVID-19 pandemic. It will determine if there is any correlation between severity of dental disease and AF incidence; test a pathway to ensure that patients are appropriately managed following detection of AF; and determine cost-effectiveness of identification of AF in dental settings.

Primary Objective:

Edinburgh Napier

• To identify the proportion of screened participants with newly identified AF in attending a dental clinic aged 65 years and older.

Secondary Objectives:

- To examine the correlation between periodontal health/disease status; age, sex; ethnicity; Index of Multiple Deprivation; and incidence of AF.

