1	This indicates that there are no pockets >3.5mm (i.e. the black band is completely visible), no calculus or plaque traps (e.g. overhanging restorations) but there is bleeding after probing		
2	This indicates that there are no pockets >3.5mm (i.e. the black band is completely visible) but there is calculus or plaque traps present		

Edinburgh Napier

3	This indicates that probing depths between 3.5mm and 5.5mm have
	been found (i.e. black band is partially visible)
4	This indicates a probing depth of >5.5mm (i.e. black band is completely hidden in pocket)
*	Indicates furcation involvement

The study team will provide a list of all participants in an encrypted excel spreadsheet (name, date of birth and address) to allow for identification to the dental hospital staff. The dental hospital will provide the result of the basic periodontal examination for each participant on an encrypted excel spreadsheet. Patients will give written consent for this data to be shared with the study team, and an appropriate data-sharing agreement will be in place between Edinburgh Napier University and Newcastle Dental Hospital.

Phase 2: healthcare professionals' interview:

Upon completion of phase one, healthcare participants will be asked to take part in an individual qualitative telephone interview with an Edinburgh Napier University researcher. A semi-structured interview schedule [Appendix 13] will be referred to in the telephone interview. We will explore the barriers and enablers to the screening processes in the AF detection programme and the effects it has had on the reported practice of the healthcare professionals involved with the participant. At the end of the interview, participants will be emailed a participant debrief sheet [Appendix 10].

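### The methods available for the periodontal-AF association are unadjusted tests and a correlation coefficient, which give no interpretable effect size for a yes/no outcome with about 16 expected cases

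*Combined protocol and SAP*

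**What the plan says.** The aim in section 2.1 includes the relation between severity of dental disease and AF. A secondary objective there is "To examine the correlation between periodontal health/disease status; age, sex; ethnicity; Index of Multiple Deprivation; and incidence of AF".

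All Phase 1 inference is in section 5.1.2. New AF is reported as a proportion with a 95% CI. Chi-square tests compare new cases by sex, and by age group or AF risk factors. For the rest, "A Pearson's or Spearman's correlation test, depending on normality of data, will be used to assess the strength" and direction of relationships between unnamed parameters. The decision rule is "A two-sided p value of < 0.05 will be considered significant". The documents contain no regression model, odds or risk ratio, or covariate set.

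Table 1 in section 4.1 codes the BPE 0 to 4, plus an asterisk that "Indicates furcation involvement". Appendix 11 records it by area of the mouth, so each person has several values. No rule reduces these to one value per person. Age and sex are collected (section 5.1.1, Appendix 11).

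**The concern.** The plan promises the strength of a relationship but offers tools that do not give it in usable form. AF is a yes/no variable and is never normally distributed, so a normality check has nothing to decide. A correlation with a rare binary outcome changes with prevalence even when the odds ratio does not, and a chi-square test yields only a p value. A reader who meets r = 0.03 may conclude that there is no relationship, when the data would be compatible with anything from a halving to a fourfold rise in the odds.

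The analysis is also entirely unadjusted. The background in section 1.1 shows why that matters: in the cited cohort, severe periodontal disease had a crude hazard ratio of 1.54, which fell in "multivariable (adjusted HR, 1.31, 95% CI, 1.06-1.62) analyses". A crude result from this study could not be set beside the adjusted one.

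With several BPE values per person and no summary rule, the exposure could be chosen after the data have been seen.

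**Working it through.** **Inputs from the documents.** n = 1000 and p = 0.016 (section 5.1.2, "assuming an incidence of 1.6" per cent), so 1000 × 0.016 = 16 expected cases; two-sided alpha 0.05; crude and adjusted hazard ratios 1.54 and 1.31 (section 1.1).

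**Inputs assumed.** The documents give no effect size or exposure share for this association. I take the share with severe disease, s, as 20%, 30% or 50%, and odds ratios (OR) of 1.54 (borrowing the size of the cited crude hazard ratio) and 3.

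**1. The plan's own figure.** Wald half-width = 1.96 × √(0.016 × 0.984 / 1000) = 0.0078, or 0.78%. The text prints "will provide a CI of 60.8" per cent; read as ±0.8%, with the sign lost when the text was extracted, it reproduces.

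**2. Correlation for a given odds ratio.** Let p0 and p1 be the AF risks without and with severe disease, solved so that the OR holds and (1−s)p0 + s·p1 = 0.016. For two binary variables, Pearson and Spearman both equal

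r = (p1 − p0) × √(s(1−s)) / √(p(1−p)).

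Example, s = 30% and OR 1.54: p0 = 0.0138, p1 = 0.0211, so r = 0.0073 × 0.458 / 0.1255 = 0.027.

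The ceiling, reached if every AF case had severe disease, is r_max = √[p(1−s) / ((1−p)s)].

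| Severe share s (assumed) | r at OR 1.54 | r at OR 3 | Ceiling |
|---|---|---|---|
| 20% | 0.024 | 0.071 | 0.26 |
| 30% | 0.027 | 0.072 | 0.19 |
| 50% | 0.027 | 0.063 | 0.13 |

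**3. Dependence on prevalence.** With s = 30% and OR 2, r is 0.044 at 1.6% prevalence and 0.16 at 50%. The odds ratio is the same and the coefficient is more than three times as large.

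**4. The coefficient as a test.** At n = 1000, |r| above about 1.96/√1000 = 0.062 gives p < 0.05. An r of 0.063-0.072 (OR 3) passes, so the null test works.

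**5. Adjustment in the cited cohort.** 1 − ln 1.31 / ln 1.54 = 1 − 0.270/0.432 = 0.37. The log hazard ratio falls by 37%.

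**6. What an odds ratio would deliver.** Unadjusted 95% CI = exp(ln 1.54 ± 1.96 × SE), with SE = √(1/a + 1/b + 1/c + 1/d) from the expected cell counts. At s = 30% the expected AF cases are 6.3 with and 9.7 without severe disease, so SE = 0.516. Power = Φ[(|p1−p0| − 1.96 × SE_pooled) / SE_unpooled].

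| s | 95% CI at OR 1.54 | Power at OR 1.54 |
|---|---|---|
| 20% | 0.51-4.66 | 15% |
| 30% | 0.56-4.23 | 15% |
| 50% | 0.56-4.23 | 13% |

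**7. Room for covariates.** At 10 to 5 events per parameter (a rule of thumb, assumed), 16 cases support 16/10 = 1.6 to 16/5 = 3.2 parameters.

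**The case against.** There are several good points on the plan's side.

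- *The BPE test is not stated.* Section 5.1.2 assigns chi-square to sex, age group and risk factors, and correlation to unnamed parameters. This stands: the mapping is inferred from the objective's wording and from the absence of any other method. It does not rescue the plan, because if the inference is wrong, part of the stated aim has no analysis.
- *The tests are valid.* A reader might infer that the correlation will always look negligible or that its p value is worthless. Neither follows. The ceiling is 0.13-0.19 at 50%-30% severe disease, an odds ratio of 3 crosses the significance threshold, and the plan sets no cut-off for a negligible r. The defect is in the effect size, not in the null test.
- *Age confounding is not shown.* A reader might assign the fall from 1.54 to 1.31 to age. Section 1.1 calls the estimate multivariable without listing its covariates, and it comes from a followed cohort, not a single screen. The fall shows that adjustment can matter, not which variable drives it.
- *Ethnicity.* A reader might infer an invalid chi-square test over all the ethnic groups in Appendix 11. Section 5.1.2 states no such test, and any error rate would rest on an assumed ethnic mix, so I make no claim about it.
- *A better model cannot make the question conclusive.* This stands, and it is why the result needs an exploratory label.

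**Conclusion.** The concern holds as a should-fix. For the periodontal-AF association, section 5.1.2 offers only unadjusted tests and a coefficient that varies with prevalence, chosen by a normality check that cannot apply to a yes/no outcome. At 1.6% AF, an odds ratio of 1.54 appears as r of about 0.03 and an odds ratio of 3 as about 0.06-0.07. No adjustment for age or sex is planned although both are available.

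These sizes rest on the plan's 1.6%, on assumed severe-disease shares of 20-50%, and on severity treated as two groups. The choice of BPE as the variable being correlated is inferred. A reader might take this as a threat to the study's main result; it is not, because the primary proportion and its CI do not depend on these tests. What is affected is a secondary objective that is also named in the aim.

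**What to change.** In section 5.1.2, before analysis:

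1. Replace the correlation for BPE and AF with logistic regression of new AF on BPE, adjusted for continuous age and sex, Firth-penalised because events are sparse. Report the odds ratio with a 95% profile-likelihood CI.
2. Pre-specify one BPE term using 1 df, for example highest sextant code 4 or asterisk versus 0-3, or a single linear score. With age and sex that makes 3 parameters, about 16/3 = 5.3 events each. A categorical five-level BPE would use 4 + 2 = 6, more than 16 cases can carry.
3. Keep participants without a scorable BPE out of code 0 and report them separately.
4. Label the analysis exploratory and state the expected precision from the working above.

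Cost: a change of wording and slightly more analysis work, possibly an SPSS extension or R, and a somewhat wider CI than the crude one. A 1-df term also gives up detail: a two-group split discards gradation, and a linear score assumes equal steps. No further participants, visits or data items are needed.
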